## 2.f Early Withdrawal of Subjects

Once enrolled, follow-up protocols will assess the presence of medication side effects and

unanticipated health events at all study visits and follow-up contacts. We will recommend dosage/use alternations as per good clinical practice if the patient experiences symptoms of nicotine toxicity or other troublesome side effects once they begin medication treatment.

Should either excessive risk to study participants and/or lack of measurable benefit to study participants be determined, the study will be stopped and all participants notified in a manner appropriate to the nature of the risk and/or lack of benefit.

## **2.g When and How to Withdraw Subjects**

We are conducting this research with strong safety measures in place (close monitoring and screening) to gather the needed data without imposing unacceptable risks. The participants will remain under the care of their own physician(s) throughout the study. To facilitate safety, participants who are not medically appropriate to take combination NRT or varenicline will not be included in the study (see exclusion criteria). Once enrolled, follow-up protocols will assess the presence of medication side effects and unanticipated health events at all study visits and follow-up contacts. We will recommend dosage/use alternations as per good clinical practice if the patient experiences symptoms of nicotine toxicity or other troublesome side effects once they begin medication treatment. We will refer patients to the study physician as needed.

Participants' medications will be continued if they have relapsed to smoking regularly. Subjects with symptoms of nicotine toxicity (including diarrhea, abdominal pain, vomiting, dizziness, and headache) reported at any research contact will be told to discontinue their medication immediately until they have a chance to discuss their symptoms with the study physician ([name]) or their primary care doctor, who will decide upon a course of action based upon the patient's status and risk (e.g., a dose reduction or medication discontinuation). Emergency care will be administered as needed. If the only severe symptom is sleep disturbance, subjects will be instructed to remove the patch at night, but otherwise keep receiving treatment according to the protocol. Should either excessive risk to study participants and/or lack of measurable benefit to study participants be determined, the study will be stopped and all participants notified in a manner appropriate to the nature of the risk and/or lack of benefit.

Any patient who reports discomfort as a result of completing the assessment of depression and anxiety will be reminded that the evaluation is discretionary, that it will be discontinued if the patient wishes, and that doing so will not affect the patient's medical care. The experienced psychiatrist investigator will be on call in case a patient has an adverse reaction to a screening or outcome evaluation. We have administered these tests to over 2,500 patients without a single subject reporting more than mild, transient emotional distress.

## **2.h Data Collection and Follow-up for Withdrawn Subjects**

For subjects who have withdrawn from the study treatment, and given consent for us to follow up, we will collect data on their basic smoking status, and adverse effects.

---

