#### 2.a Inclusion Criteria

Inclusion:

- 1) Adult (>=21 years of age), seeking treatment for smoking cessation.
- 2) Able to speak English,
- 3) Active smoking (Cigarettes Per Day (CPD) >=5) and exhaled CO >=8 ppm
- 4) Agree to participate in this randomized smoking cessation trial with follow up assessments up to 12 months, and

---

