#### **E4 Visit 2-9**

At Follow up visits at the last day pre-quit, quit date, 1 week, 2 weeks, 4 weeks, 3 months, 6 months, and 1 year after the quit date, administer follow up assessments.

At follow up visits, all participants will receive the follow up visit assessment.

The follow up assessment by phone includes the following:

Smoking Status  
Non-study treatment data  
Patch/Lozenge/Pill use and potential side effects  
Adherence  
Medical History  
Environmental factors  
Adverse Events Screener  
WSWS

At the in-office follow up visits at 12 weeks and 6 months post-quit, the subject will provide a breath sample for alveolar CO level.

In follow visits up to 12 weeks after quit date, subjects receive smoking cessation counseling. This session will be the final counseling session.

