### ***E5 Study Outcome Measurements and Ascertainment***

**Smoking Status and Withdrawal:** All subjects will be contacted via phone for assessments of smoking status. We will assess long term outcomes following the SRNT Workgroup recommendations (Hughes et al, 2003).

Primary Outcome Measure:

7-day point prevalence abstinence [Time Frame: Week 12]

The definition of this measure requires: (a) no self-reported smoking (not even a puff of a cigarette) for at least the 7 days prior to the assessment, and (b) CO biochemical verification of abstinence.

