### ***F3 Analysis Plan***

All analyses will first be conducted separately for European Ancestry (EA) and African American (AA) due to distinctly different allele frequencies and linkage disequilibrium across ancestry. If consistent genetic effects are seen across ancestry, samples of EA and AA ancestry will be combined in analyses with the covariate of race.

---

We will compare the abstinence outcome in the two placebo groups (placebo nicotine patch plus placebo nicotine lozenge vs. placebo varenicline pill). If they are comparable which is consistent with prior experience of other placebo-controlled smoking cessation trials, they will be pooled for further analyses.

The primary outcome is CO-confirmed point prevalent abstinence at end of treatment (12 weeks), defined if subjects deny smoking during 7 days prior of the end of treatment and provide a breath sample with CO <8 ppm.

Hypothesis #1 is to examine whether medication effect (cNRT vs. placebo) varies with CHRNA5 (i.e. a genotype X medication interaction). A series of generalized linear models will be used to examine main effects of genotype (rs16969968) and medication before testing genotype x medication interactions, with sex, age, and study cohort as covariates using logistic regression models.

Hypothesis #2 is to examine whether medication effect (varenicline vs. placebo) varies with CHRNA5 (i.e. a genotype X medication interaction). A series of generalized regression models will be used to examine main effects of genotype (rs16969968) and medication before testing genotype x medication interactions, with sex, age, and study cohort as covariates using logistic regression models.

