## ***F5 Missing Outcome Data***

If a participant prematurely discontinues the study medication, the reason for discontinuation will be determined and classified as primarily due to an adverse event, or lack of efficacy, not wanting to take another medication, or others. We will examine missing data for causes and compare the groups with respect to side effects and efficacy. We will adhere to the intent-to-treat principle for smoking outcome analyses, so that dropouts will be treated as smoking. In addition, we will analyze the missing data under conditions of both missing completely at random (MCAR) and missing at random (MAR), and use appropriate strategies such as imputation when appropriate.

Participants who drop off the trial before they get a dose of the study medication/placebo will be included in the analyses of efficacy if they receive the medication packet. They will be included in the safety analyses if medication was dispensed to them. We will ensure an appropriate informed consent process to minimize the probability of drop out. We will also assess level of adherence to the study protocol and these information will be available for use in secondary analyses.

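### The rule for participants withdrawn from study treatment (2.h) conflicts with the all-participant follow-up and CO schedule, and if followed as written leaves abstinent stoppers with no route to success on the primary outcome

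*Combined protocol and SAP*

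**What the plan says.** Section 2.h addresses participants withdrawn from study treatment, as distinct from the study: "For subjects who have withdrawn from the study treatment, and given consent for us to follow up, we will collect data on their basic smoking" […]. The items it names are smoking status and adverse effects. CO and timeline follow-back are not mentioned.

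Other sections are wider:

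- Inclusion criterion 4 requires candidates to "Agree to participate in this randomized smoking cessation trial with follow up assessments up to 12 months".
- E4: "At follow up visits, all participants will receive the follow up visit assessment". No exception is made for people off medication.
- The E2 schedule lists the follow-up assessment, including timeline follow-back, through Visit 9. Its footnote makes CO at Visits 7 and 8 depend on self-reported abstinence, not on medication status.

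The primary outcome, in C3 and E5, needs seven days without self-reported smoking plus "CO biochemical verification of abstinence". F3 requires that the participant "provide a breath sample with CO <8 ppm" at 12 weeks.

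On missing outcomes, F5 says: "We will adhere to the intent-to-treat principle for smoking outcome analyses, so that dropouts will be treated as smoking". It adds that "we will analyze the missing data under conditions of both missing completely at random (MCAR) and missing at random (MAR"), with imputation where appropriate. It does not define a dropout.

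**The concern.** Read on its own, 2.h sets a reduced data collection for people who have come off study treatment. The primary outcome has two limbs, and the second is a CO reading. A participant who stops in week 3 because of a side effect, stays abstinent and is followed by self-report alone cannot satisfy that limb. Without timeline follow-back, the dates needed for days to lapse and days to relapse are also missing.

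The protocol's own text makes unequal stopping across arms plausible. Section 2.g tells participants with symptoms such as vomiting or headache to stop medication pending physician review, and C3 lists those two among the agonist-related side effects. F5 also names lack of efficacy as a reason for discontinuation, and that could be commoner on placebo. If stopping differs by arm, the measured drug effects shift. If it differs by genotype and arm together, the genotype-by-medication interaction, which is the trial's question, can shift too. A CO reading not taken at week 12 cannot be obtained later.

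**Working it through.** **Step 1. Set the texts side by side for one person: off treatment, reporting abstinence at week 12.**

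- Under E4 and the E2 footnote: assessed, CO test due, can count as abstinent.
- Under 2.h as written, with consent to follow-up: smoking status and adverse effects collected, CO not named. With no CO the person cannot count as abstinent.
- Under 2.h as written, without that consent: nothing collected. F5 would score the person as smoking if this makes them a dropout.

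The documents do not say whether 2.h overrides E2 and E4, whether stopping medication makes someone a dropout, or how self-reported abstinence without CO is scored.

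**Step 2. Inputs for an illustration.** The plan has no figure on this point to reproduce.

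- From the documents: placebo abstinence 20% (F1); 822 randomised 1:1:1, so 822/3 = 274 per arm; two-sided alpha 0.05.
- Assumed: a true medication odds ratio of 2.00. Placebo odds are 0.20/0.80 = 0.25, active odds 0.50, active abstinence 0.50/1.50 = 33.3%.
- Assumed: proportion stopping, d, of 10% to 30%; share of abstinent stoppers without CO, s, of 0.5 to 1; abstinence in stoppers relative to the arm average, r, of 0.5 to 1.

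**Step 3. Formula.** Observed abstinence = p × (1 − d × s × r). If s = 0, so that E2 and E4 are followed, observed abstinence equals p and there is no bias.

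**Step 4. Worked case, s = r = 1, stopping 30% active and 10% placebo.** Active: 0.333 × 0.70 = 0.233. Placebo: 0.20 × 0.90 = 0.180. Observed odds ratio = (0.233/0.767)/(0.180/0.820) = 1.39.

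**Step 5. Range.** Power is for a simple two-arm comparison with 274 per arm. It is 0.94 with no loss.

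| Stopping, active / placebo | Observed OR (true 2.00) | Power |
|---|---|---|
| equal, 10% to 30% | 1.99 to 1.87 | 0.94 to 0.80 |
| 30% / 10% | 1.84 to 1.39 | 0.87 to 0.34 |
| 10% / 30% | 2.12 to 2.63 | 0.97 to over 0.99 |

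The first figure in each cell has the smallest loss (s = r = 0.5); the second has the largest (s = r = 1).

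**Step 6. Interaction.** Suppose the true odds ratio is 2.00 in two genotype groups, so the true ratio of odds ratios is 1.

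- Active-arm stopping 30% in one group and 10% in the other, placebo stopping 10% in both: 1.84/1.99 = 0.93 with the smallest loss; 1.39/1.95 = 0.71 with the largest.
- Stopping 30% in both arms of one group and 10% in both arms of the other: 1.96/1.99 = 0.99 to 1.87/1.95 = 0.96.

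A material distortion therefore needs stopping to differ by genotype and arm jointly.

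**The case against.** The strongest reply is that E4 and the E2 footnote already entitle the abstinent stopper to a CO test, and that a list of what 2.h collects is not a ban on anything else. E5 describes CO validation within the ascertainment of smoking status, so that term might be read to include it. F5 keeps participants who never took a dose in the efficacy analysis if they received the packet, so being off drug does not by itself remove anyone. All of this stands. It is why the defect is a conflict between sections and not an established loss of data.

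A reader might go further and infer four things that the documents do not support:

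- *Stopping medication is a near-automatic failure.* That follows only if 2.h overrides E2 and E4, which no section says.
- *A separate consent is required after stopping.* Section 2.h does not say whether it means a new consent or the enrolment one, and the consent form is not available.
- *2.h is the only rule that bears on stoppers.* F5 classifies reasons for discontinuation, D3 3.b carries NRT dose changes and discontinuation into the adherence analyses, and E4 covers everyone. In addition, 2.g describes pauses and dose reductions, so not every interruption is a withdrawal from treatment.
- *Both drug effects are biased toward the null.* That needs more stopping on active drug. The direction reverses if placebo participants stop more often.

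The MCAR and MAR analyses in F5 are relevant, but they are additional to the analysis that scores dropouts as smoking, and they cannot recover a reading never taken. Attachment K10, the detailed SAP, appears only as a heading, so a scoring rule for abstainers without CO may exist there.

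**Conclusion.** The concern holds as an unresolved conflict. Section 2.h, as written, restricts follow-up after withdrawal from treatment in a way that does not fit E2, E4 or the intent-to-treat principle in F5. Staff who follow it literally would leave abstinent stoppers unable to meet the primary outcome.

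The size and direction of the resulting bias are unknown. It is nil if E2 and E4 are followed, small if stopping is balanced, toward the null if stopping is commoner on active drug, and away from the null if commoner on placebo. The interaction could be distorted if stopping differs by genotype and arm. The figures above rest on assumed stopping rates, an assumed odds ratio and an assumed share of abstinent stoppers without CO; only the 20% placebo rate, the sample size, the allocation and alpha come from the plan. Confidence is high that the texts conflict and moderate at best on how much it matters. Because the primary outcome's ascertainment depends on it, the conflict should be settled in the protocol text.

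**What to change.** Rewrite 2.h so that participants who stop study medication for any reason stay on the full E2 schedule, Visits 2 to 9. This includes timeline follow-back, and the CO test at Visits 7 and 8 if they report abstinence. Collection ends only if the participant withdraws consent for follow-up, with date and reason recorded. Check that the enrolment consent form supports this before adopting the wording.

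Record stopping medication and withdrawing from follow-up as two separate statuses. In F5, state that stopping medication alone does not make a participant a dropout. Unless K10 already does so, add a scoring rule and a sensitivity analysis for self-reported abstinence without CO.

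Separately, F2 tells participants who smoke at least 5 cigarettes daily to discontinue study medication, while 2.g, 4.b and H1 have participants who smoke regularly continue it. These passages must be reconciled, since they change how many people fall under 2.h.

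The cost is a wording change plus payments and tests already in the plan. Under I4, a retained stopper receives $20 each for Visits 7 and 8, a further $20 for each in-person verification, and $10 for Visit 9: at most 2 × $40 + $10 = $90, and $50 if no verification visit is needed.

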## **D3 Study Drug**

### **3.a Description**

The participants will be randomized with the ratio 1:1:1 to the treatment arm of combination NRT (nicotine patch and lozenge) plus smoking cessation counseling, the treatment arm of varenicline plus counseling, or to the treatment arm of placebo (patch and lozenge or pill) plus smoking cessation counseling.

### **3.b Treatment Regimen**

During the baseline visit (visit 1), all participants will be randomized at 1:1:1 to 1) one arm of combination nicotine and smoking cessation counseling, or 2) varenicline and smoking cessation counseling, and 3) another arm of placebo and smoking cessation counseling at no cost to participants. Participants will receive enough patches to last 12 weeks. The duration of medication treatment is 12 weeks (standard for participants who smoke >9 cigs/day=8 weeks of 21mg, 2 weeks of 14mg, and 2 weeks of 7mg nicotine patches; standard for participants who smoke 5-9 cigs/day=8 weeks of 14mg and 4 weeks of 7mg;).

**Nicotine Lozenge:** The 4 mg dosage is recommended for patients who take their first cigarette within 30 minutes of waking and the 2mg dosage is recommended for patients who take their first cigarette more than 30 minutes after waking. Participants will begin taking lozenges a week before abstinence to replace some cigarettes. Participants will then take 1 lozenge every 1-2 hours for 6 weeks, then 1 lozenge every 2-4 hours for 3 weeks, and 1 lozenge for every 4-8 hours for 3 weeks. Participants will be encouraged to take a minimum of 4 pieces/day unless this amount produces adverse effects.

**Varenicline:** Varenicline will be initiated with a titration for 7 days before the quit date. Before the quit date, participants will take one 0.5mg tablet daily for 3 days, then two 0.5mg tablets for 4 days (one in the morning and one in the evening). After the quit date (day 8), participants will take 1mg tablet in the morning and in the evening.

**Placebo:** 50% of participants assigned to the placebo group will receive placebo patch/lozenge, and 50% will receive the placebo pill as a control for the two active medication arms.

All participants will be given complete instructions on proper medication use, and will be urged to contact his/her physician and a study hotline number immediately in case of listed symptoms of nicotine toxicity or side effects. Dose changes or discontinuation of NRT may be recommended; all changes will be addressed in analyses of adherence outcomes.

### **3.c Method for Assigning Subjects to Treatment Groups**

The participants will be randomized with the ratio 1:1:1 to one treatment arm of combination NRT plus smoking cessation counseling, one treatment arm of varenicline plus counseling, or to placebo plus smoking cessation counseling.

Participants will be randomly assigned to each of the 3 arms. SAS Version 9 statistical software will be used to generate the random assignment table. The group assignment will be coded to ensure that the double blind is maintained, and the interface will prevent staff from having

access to the participant's assignment until after the baseline and post treatment assessments have been completed. Adequacy of blinding will be tested and different raters will assess efficacy vs. safety to ensure blinding.

### **3.d Preparation and Administration of Study Drug**

During the baseline visit (visit 1), all participants will be randomized at 1:1:1 to each of the 3 arms described above and receive treatments at no cost to participants.

### **3.e Subject Compliance Monitoring**

Subjects will be asked to report their use of medication in each follow up visit during the 3 month medication treatment period.

### **3.f Prior and Concomitant Therapy**

Subjects currently taking the medication Bupropion, Wellbutrin, Zyban, will be excluded.

**Non-Study Treatment:** Patients will be asked to refrain from non-study smoking cessation interventions such as intensive smoking cessation counseling and smoking cessation medication during treatment. Non-Study Treatment data will be assessed at each follow up visit to document whether the patient is receiving any non-study treatment for smoking cessation or other medical conditions, including medications, counseling, quit line, support groups, self-help books, and complementary/ alternative medicine remedies.

### **3.g Packaging**

The study medication (Nicotine patch and place patch, varencliline, and placebo (patch and lozenge or pill) will have identical packaging when they are provided to the participants.

### **3.h Blinding of Study Drug**

The group assignment will be coded to ensure that the double blind is maintained, and the interface will prevent staff from having access to the participant's assignment until after the baseline and post treatment assessments have been completed.

### **3.i Receiving, Storage, Dispensing and Return**

Participants will receive their study medication when they attend the in office visit 1 (baseline).

## **E Study Procedures**

### ***E1 Screening for Eligibility***

We propose to enroll previous participants of the COGEND study and the GERS study and to expand enrollment opportunities to the community, by recruiting from the volunteers for health program in our University Hospital System, and smokers interested in smoking cessation in the local community. We expect we can successfully recruit 822 patients in 3 years.

#### Step 1. Screening of Potentially Eligible Subjects

The PI or research assistant will need to access the following data element.

- 1) Subject agreed to be contacted to participate in a smoking cessation trial.

#### Step 2. Ask the potential participant the following screening questions to determine eligibility.

- 1) How many cigarettes do you smoke a day?
- 2) Are you committed to participating in this study on treatment for smoking cessation for a full year?
- 3) Are you willing to use birth control for 2 months while you are receiving medication treatment for smoking cessation? (ONLY for pre-menopausal women)
- 4) Are you pregnant or breast feeding? (ONLY for pre-menopausal women)
- 5) Do you currently take the medication Bupropion, Wellbutrin, Zyban, Varenicline, or Chantix?
- 6) Are you allergic to the Nicotine Patch, lozenge, or varenicline?
- 7) Have you had significant cardiac conditions (heart attack, unstable angina, coronary angioplasty, cardiac bypass) in the past 6 months?
- 8) Do you currently drink alcohol at the level of at least 6 drinks/day, 6 days/week?
- 9) Have you had active depression or psychosis in the past 12 months?
- 10) Do you currently have thoughts of suicide or have a prior suicide attempt in the past 12 months?
- 11) Do you have end stage kidney disease requiring hemodialysis?

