## 2.a Exclusion Criteria

### Exclusion:

The subject will be excluded for having a condition that prevents him/her from effectively participating in the protocol.

- 1) Pregnancy or breast feeding,
- 2) Active use or recent use (<= to 1 month) of medication or e-cigarettes for nicotine dependence/smoking cessation, or use of e-cigarettes for more than 9 days in the prior month
- 3) Allergy to Nicotine patch, Nicotine lozenge, or varenicline
- 4) Unwillingness to prevent pregnancy during the medication phase and 1 month afterwards (women only),
- 5) Significant cardiac conditions (myocardial infarction (heart attack), unstable angina, coronary angioplasty, cardiac bypass) or serious arrhythmia within 6 months
- 6) Current heavy alcohol consumption (greater than or equal to 6 drinks/day, 6 days/week)
- 7) Active psychosis or poorly controlled depression in the past 6 months
- 8) Any suicide attempt or poorly controlled depression in the past 6 months,
- 9) End stage renal disease with hemodialysis

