### Step 2. Ask the potential participant the following screening questions to determine eligibility.

- 1) How many cigarettes do you smoke a day?
- 2) Are you committed to participating in this study on treatment for smoking cessation for a full year?
- 3) Are you willing to use birth control for 3 months while you are receiving medication treatment for smoking cessation and one month after? (ONLY for pre-menopausal women)
- 4) Are you pregnant or breast feeding? (ONLY for pre-menopausal women)
- 5) Do you currently take the medication Bupropion, Wellbutrin, Zyban, Varenicline, or Chantix, or nicotine patch or lozenge?
- 6) Are you allergic to the Nicotine Patch, lozenge, or varenicline?
- 7) Did you have significant cardiac conditions (an acute heart attack, unstable angina, coronary angioplasty, cardiac bypass) in the past 6 months?
- 8) Do you currently drink alcohol at the level of at least 6 drinks per day, 6 days per week?

---

- 9) Have you had active depression or psychosis in the past 6 months?
- 10) Do you currently have thoughts of suicide or have a suicide attempt in the past 6 months?
- 11) Do you have end stage kidney disease requiring hemodialysis?

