#### Step 4. Obtain Informed Consent

Patients who express interest in participating will be informed in greater detail about the study and receive screening for eligibility criteria by the PI psychiatrist or the research assistant. The patients will learn about general requirements for participation (e.g., need for follow-up, participation in assessments, etc.) as well as risks associated with nicotine toxicity, nicotine withdrawal, blood sample and pharmacotherapy. If still interested and eligible, the patients will then be asked to provide written informed consent to participate, on a form approved by the Washington University School of Medicine Institutional Review Board. Study candidates will read the informed consent document and be given an opportunity to ask any questions regarding study participation. They will also complete the consent form. A follow up contact can be scheduled if potential participants would like to have more time to consider participation. Participants will receive a signed copy of the consent document.

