#### Step 3. Obtain Informed Consent

Patients who express interest in participating will be informed in greater detail about the study and receive screening for eligibility criteria by the PI psychiatrist or the research assistant. The patients will learn about general requirements for participation (e.g., need for follow-up, participation in assessments, etc.) as well as risks associated with nicotine toxicity, nicotine withdrawal, blood draw, and pharmacotherapy. If still interested and eligible, the patients will then be asked to provide written informed consent to participate, on a form approved by the Washington University School of Medicine Institutional Review Board. Study candidates will read the informed consent document and be given an opportunity to ask any questions regarding study participation. They will also complete the HIPAA form and the consent form. A

follow up contact can be scheduled if potential participants would like to have more time to consider participation. Participants will receive a signed copy of the consent document.

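### The E1 screening script asks for 2 months of birth control, which is shorter than the time on study drug and about half of what exclusion criterion 4 requires; its Q5, Q9 and Q10 also depart from the criteria

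*Combined protocol and SAP*

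**What the plan says.** The protocol carries two versions of the pre-consent screening questions, one in D2 2.c (Step 2) and one in E1 (Step 2). Both are headed as the questions that settle eligibility, and both are current text.

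On contraception:
- D2 2.a, exclusion criterion 4: "Unwillingness to prevent pregnancy during the medication phase and 1 month afterwards" (women only).
- D2 2.c, Q3: "Are you willing to use birth control for 3 months while you are receiving medication treatment for smoking cessation and one month after".
- E1, Q3: "Are you willing to use birth control for 2 months while you are receiving medication treatment for smoking cessation", with nothing about the period after treatment.

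On treatment length, D3 3.b states "The duration of medication treatment is 12 weeks". The same section adds a pre-quit week for two products: "Participants will begin taking lozenges a week before abstinence to replace some cigarettes" and "Varenicline will be initiated with a titration for 7 days before the quit date". The lozenge schedule then runs 6 + 3 + 3 weeks after the quit date.

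On the other items:
- **Q5.** 2.c asks about bupropion, varenicline and nicotine patch or lozenge. E1 asks about bupropion and varenicline only. Criterion 2 excludes current use, or use within the past month, of any cessation medication.
- **Q9 and Q10.** E1 looks back 12 months for depression or psychosis and for a suicide attempt. Criteria 7 and 8 and the 2.c script look back 6 months.

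**The concern.** A screening question should let staff decide whether the criterion is met. E1 Q3 does not. A woman willing to use contraception for two months but no longer would answer yes truthfully and still meet exclusion criterion 4. The uncovered time includes weeks on study drug as well as the month after. The documents name no pregnancy test in the visit schedule or visit lists, so these questions are the main pregnancy safeguard that can be seen in the text.

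The two other mismatches are secondary and run in opposite directions:
- Q5 in E1 is too loose. Someone already using a nicotine patch or lozenge is not asked about it, which matters in a placebo-controlled trial with a combination-NRT arm.
- Q9 and Q10 in E1 are too strict. They could turn away people whose episode was 6 to 12 months ago and whom the criteria allow. That is over-exclusion and not a safety gap.

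With two scripts in force, who is eligible can depend on which one staff read from.

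**Working it through.** The plan gives no figure to reproduce on this point. The check compares durations and then sets the items side by side.

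**Inputs**
- E1 Q3: 2 months, taken as about 61 days.
- Medication phase (D3 3.b): 12 weeks = 84 days. With the pre-quit week, the lozenge schedule gives 1 + 6 + 3 + 3 = 13 weeks = 91 days. The adherence outcome in C3 also counts from the pre-quit week to week 12.
- Month after treatment (criterion 4): 30 days.

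**Required period** = medication phase + 30 days
- 12 weeks: 84 + 30 = 114 days
- 13 weeks: 91 + 30 = 121 days

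**On drug but not asked about** = medication phase − 61
- 12 weeks: 84 − 61 = 23 days; 23/84 = 27%
- 13 weeks: 91 − 61 = 30 days; 30/91 = 33%

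**Total not asked about** = required period − 61
- 12 weeks: 114 − 61 = 53 days; 53/114 = 46%
- 13 weeks: 121 − 61 = 60 days; 60/121 = 50%

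**Same check for 2.c**: 3 months (about 91 days) + 30 = 121 days, so the shortfall is 0 even on the 13-week reading.

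**Sensitivity to the length of a month.** With a month of 365.25/12/7 = 4.35 weeks, 2 months is 8.7 weeks. That is 3.3 weeks short of 12 weeks and 4.3 short of 13. The required period is 16.3 to 17.3 weeks, and E1 covers 53% to 50% of it. The conclusion does not depend on the rounding.

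**Items side by side**

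| Item | Criteria (2.a) | Script in 2.c | Script in E1 |
|---|---|---|---|
| Birth control | Medication phase + 1 month | 3 months + 1 month | 2 months |
| Current patch or lozenge | Excluded (criterion 2) | Asked | Not asked |
| Depression or psychosis look-back | 6 months | 6 months | 12 months |
| Suicide attempt look-back | 6 months | 6 months | 12 months |

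On these specific points 2.a and 2.c agree, and E1 is the one that differs.

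**The case against.** The best defence is that the script is not the last gate. Criterion 4 is stated correctly. In E1 itself, Step 3 has interested people "receive screening for eligibility criteria by the PI psychiatrist or the research assistant", and 2.c Step 4 says "If still interested and eligible, the patients will then be asked to provide written informed consent to participate". Several sections (for example E4 4.b and F2) repeat that participants must meet the criteria. On that reading, a woman unwilling for the full period is still excluded by the protocol, whatever E1 Q3 says. The screening log (K7) and consent form (K1) are listed but their text is not available, so nobody can say from the documents which wording is read out. D3 3.f also asks participants to avoid non-study cessation medication during treatment and records it at follow-up.

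This limits the likely harm, and that part stands. It does not rescue the question. A general duty to meet the criteria does not repair a specific item that gives the wrong duration, and unseen attachments cannot be assumed to correct it. The instruction in 3.f applies during treatment and does not screen at entry.

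Two further points are fair:
- No rule says that a yes to Q9 or Q10 excludes automatically, so the most one can say is that the 12-month windows could turn people away.
- The 2.c script is not a perfect match to 2.a either. It asks only about current medication, omits e-cigarettes and arrhythmia, asks about active rather than poorly controlled depression, and adds current suicidal thoughts. E1 shares these gaps, so they do not excuse its own.

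**Conclusion.** The concern holds, and it rests mainly on Q3. E1 asks for about 61 days of contraception where criterion 4 needs 114 to 121. No reading of the treatment regimen makes two months cover even the time on drug. The lower figures use the stated 12 weeks. The upper ones count the pre-quit week in addition, which the lozenge schedule spells out; for varenicline, 3.b gives the pre-quit week but no end date. The shortfall remains on either reading.

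The Q5 omission and the 12-month windows in Q9 and Q10 are genuine but secondary.

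This is a gap in wording, not measured exposure. The documents do not allow an estimate of how many women would be affected. Nothing here touches the endpoint, the analysis, the sample size of 822 or the stated power of 0.84.

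**What to change.** Delete the Step 2 questions from E1 and refer to the 2.c script, so that only one version exists. If both are kept, edit E1 as follows:
- Q3: three months during treatment plus one month after.
- Q5: add nicotine patch and lozenge.
- Q9 and Q10: change 12 months to 6.

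It would be sensible, though optional, to use the same amendment to bring the 2.c script closer to 2.a. Add past-month cessation medication and e-cigarette use (criterion 2) and serious arrhythmia within 6 months (criterion 5), and settle the wording on depression and suicidal thoughts in one place. Check that the screening log and consent form carry the same contraception period.

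The cost is a minor amendment and brief staff retraining, with no added visits, procedures or participants.
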